# 8 GENERAL STATISTICAL CONSIDERATIONS

#### 8.1 Determination of Sample Size

No prior data are available on which to base assumptions for sample size/power considerations. The results of this pilot study will be used to design future studies, and the sample size of approximately 20 subjects is deemed to be appropriate for this purpose.

#### 8.2 Statistical Software

Statistical analyses will be performed using SAS (SAS Institute, NC, USA). Cholesterol efflux capacity and percent (%) fat in liver assessed by MRI will be reported and calculated by EXCEL.

#### **Summary Statistics**

Data will be summarized with respect to disposition, demographics, pre-treatment characteristics, safety outcomes, tolerability, and efficacy outcomes. Summary statistics for continuous variables will include the number of subjects, the mean, median, standard deviation, and range. For categorical data, summaries will include counts and percentages.

Biomarkers and clinical outcomes will be summarized longitudinally from baseline to Week 8 or Week 12, with means and standard deviations at each timepoint.

#### 8.3 Precision

Results will be reported to 3 significant figures. Percentages will be reported to 0.1 percentage points. *P*-values will be reported to two digits when  $\geq$  .095, to three digits when  $\geq$  .00095 and < .095, and as < .001 for all smaller values.

# **9 ANALYSIS POPULATION**

Population	Description
All Subjects	All subjects enrolled
Safety Analysis Set	All subjects who received at least one dose of study drug and had at least one post dose safety assessment.
Intent-to-treat Set	All randomized subjects in the groups to which they are randomly assigned, regardless of their adherence to the inclusion-exclusion criteria, regardless of the treatment they actually received, and regardless of subsequent withdrawal from treatment or deviation from the protocol.
Per Protocol Set	All subjects who received at least one dose of study drug and no major protocol deviations.
PK population	All subjects who received at least 1 dose of study drug (MN-001) and have evaluable PK data, and complete scheduled post-dose PK measurements without protocol deviations, violations, or events include, but may not be limited to, vomiting occurring within 30 minutes following oral dosing, sample processing errors that lead to inaccurate bioanalytical results, and/or inaccurate dosing on the day of PK sampling. In the case of a significant protocol deviation, PK data collected during the affected treatment period will be excluded from summary statistics but will be included in individual subject listings.

For purposes of analysis, the following sets are defined:

# **10 DEMOGRAPHIC AND BASELINE CHARACTERISTICS**

Two listings will be presented for Subject Disposition and Major Protocol Deviations as defined below.

### **10.1** Subject Disposition

All enrolled subject disposition will be presented.

Number of subjects in the following categories will be summarized as appropriate:

- Enrolled
- Safety Population
- PK Population

Additionally, a summary on study completion status will be presented:

- Completed study among subjects enrolled;
- Prematurely discontinued the study and the reasons for discontinuations as follows:
  - Adverse Event
  - Informed Consent Withdrawn
  - Lost to Follow-Up
  - Other reason, specify

#### **10.2 Protocol Deviations**

The following will be considered as major protocol violations:

Protocol deviations are collected and will further be evaluated by the sponsor to determine whether the violation affects the efficacy and/or safety measurements for the subject.

Major deviations will be defined as the following:

- Eligibility Criteria not met any deviation from the inclusion / exclusion criteria in the protocol will be considered major
- Informed consent missing consent
- Dose administration errors
  - Incorrect (high, low) dose administered to subject
- Unreported SAEs
- Any other instance in the opinion of the sponsor and investigator that adversely affects the safety of the subject or the integrity of the study data

### **10.3 Demographics and Baseline Characteristics**

Demographic and baseline characteristics will be summarized for all subjects, including age, sex, race, ethnicity, Fib-4 Index score, and NAFLD score. Summary statistics (e.g., number of subjects, mean, median, standard deviation, and range) will be generated for continuous variables (e.g., age and weight) and the number and percentage of subjects within each category will be presented for

categorical variables (e.g., gender, ethnicity, and race). Age will be presented as captured in the Screening visit CRF.

### 10.4 Medical History

Medical and surgical history will be coded according to the latest version of MedDRA and summarized by system organ class and preferred term.

### 10.5 Prior and Concomitant Medication

Medications used in this study will be coded by using the World Health Organization Drug Dictionary Enhanced and categorized as follows:

**Prior medication** is any medication that started before initial dosing of study drug, regardless of when it ended.

**Concomitant medication** is any medication received at or after the dose of study drug, medication that was received before initial dosing and continued after initial dosing of study drug, or medication with missing stop date.

A given medication can be classified as a prior medication or a concomitant medication or both. If a medication has a missing or partial missing start/end date or time and it cannot be determined whether it was taken before initial dosing or concomitantly, it will be considered as both prior and concomitant.

# **11 EFFICACY ANALYSIS**

### 11.1 Serum Triglyceride Level

The primary endpoint is to evaluate the effects of MN-001 on serum triglyceride level in NASH and NAFLD with hypertriglyceridemia. The serum triglycerides will be measured as the difference after 8 weeks of treatment from pre-treatment serum triglyceride levels. Pre-treatment triglyceride level will be defined as the highest value of serum triglyceride at screening visit or baseline visit. The data are expressed as the percent change from the baseline value and calculated using the equation: Change = [100%\*(Endpoint value - Baseline Value)/Baseline Value].

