# **10. ASSESSMENT OF EFFICACY**

#### **10.1. Primary Endpoints**

The primary endpoint, cholesterol efflux, will be calculated as the percent of cholesterol removed from the cells and appearing in the culture medium normalized to a reference serum pool. The ability of serum HDL to remove cholesterol from cultured cells will be assessed as an *in vitro* method to evaluate functional changes in HDL mediated by changes due to MN-001 treatment.

Cholesterol efflux with HDL will be measured by Cholesterol Efflux Fluorometric Assay Kit (BioVision, Inc.). Detailed protocol is attached in Appendix 3.

An additional primary endpoint is will evaluate the effects of MN-001 on triglyceride level in subjects with NAFLD or NASH. The primary endpoint will be decreased triglycerides measured as the difference after 12 weeks of treatment from baseline levels. The data are expressed as the percent change from the baseline value and calculated using he equation: Change = [100%\*(Endpoint value - Baseline Value)/Baseline Value]

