### 6.2 Study Endpoints (Outcome Variable)

### **Co-Primary Outcome Variables**

• Mean change from baseline on serum triglyceride levels at Week 8

The primary endpoint is to evaluate the effects of MN-001 on serum triglyceride level in NASH and NAFLD with hypertriglyceridemia. The serum triglycerides will be measured as the difference after 8 weeks of treatment from pre-treatment serum triglyceride levels. Pre-treatment triglyceride level will be defined as the highest value of serum triglyceride at screening visit or baseline visit. The data are expressed as the percent change from the baseline value and calculated using he equation: Change = [100%\*(Endpoint value - Baseline Value)/Baseline Value]

• Mean change from baseline on cholesterol efflux capacity at Week 12

Cholesterol efflux capacity in the subjects will be quantified at National Institute of Biomedical Innovation, Osaka, Japan using the method previously reported (Ogura et al 2016). Percent efflux will be calculated by the following formula:  $[(\mu Ci of 3H-cholesterol in mediums containing 2.8% apolipoprotein B-depleted serum -\mu Ci of 3H-cholesterol in serum-free mediums)/\mu Ci of 3H-cholesterol in cells extracted before the efflux step] × 100. All assays will be performed in duplicate. To correct for inter-assay variation across plates, a pooled serum control from eleven healthy volunteers was included on each plate, and values for serum samples from patients were normalized to the value of the pooled sample in subsequent analyses.$ 

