### 7.3 Randomization and Blinding

This is an open-label study; therefore, randomization and blinding are not applicable.

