### 11.3 Other Secondary Efficacy Analysis

Other secondary measures, lipid profile including serum HDL-C, LDL-C, total cholesterol level, liver enzymes (ALT and AST) will be measured by the change from baseline to Week 8 and Week 12. The percentage (%) of fat in the liver assessed by MRI will be measured by the changes from baseline MRI to post treatment MRI.

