# **15 TABLES AND LISTINGS**

### 15.1 Table of Tables

Table Number	Table Description		
14.1	Demographic Data		
14.1.1	Subject Disposition (including discontinued subjects)		
14.1.2	Summary of Protocol Deviations		
14.1.3	Demographics and Baseline Characteristics		
14.1.4	Summary of Medical History		
14.1.5	Prior and Concomitant Medications (Safety Population)		
14.1.6	Study Drug Exposure		
14.2	Efficacy		
14.2.1	Summary of Serum triglyceride – Mean Change from Baseline to Week 8		
14.2.2	Summary of Serum Lipid Panel – Mean Change from Baseline to Week 8		
14.2.3	Summary of Liver Enzymes (ALT, AST) – Mean Change from Baseline to Week 8		
14.3	Safety Data		
14.3.1	Display of Adverse Events		
14.3.1.1	Number of Treatment-Emergent Adverse Events by System Organ Class and Preferred Term (Safety Analysis Set)		
14.3.1.2	Number of Subjects with Treatment-emergent Adverse Events by System Organ Class and Preferred Term (Safety Analysis Set)		
14.3.1.3	Number of Subjects with Treatment-emergent Adverse Events by System Organ Class, Preferred Term, and Intensity (Safety Analysis Set)		
14.3.1.4	Number of Subjects with Treatment-emergent Adverse Events by System Organ Class, Preferred Term, and Relationship (Safety Analysis Set)		
14.3.1.5	Number of Subjects with Treatment-emergent Serious Adverse Events by System Organ Class and Preferred Term (Safety Analysis Set)		
14.3.1.6	Number of Subjects with Treatment-emergent Adverse Events Leading to Study Discontinuation by System Organ Class and Preferred Term (Safety Analysis Set)		
14.3.2	Listings of Serious and Significant Adverse Events		
14.3.3	Narratives of Serious and Certain Other Significant Adverse Events		
14.3.4	Abnormal Laboratory Value Listing (Each Subject)		
14.3.4.1	Summary of Hematology by Visit (Safety Analysis Set)		
14.3.4.2	Hematology – Shift from Baseline by Visit (Safety Analysis Set)		
14.3.4.3	Summary of Serum Chemistry by Visit (Safety Analysis Set)		
14.3.4.4	Serum Chemistry – Shift from Baseline by Visit (Safety Analysis Set)		
14.3.4.5	Summary of Vital Signs by Visit (Safety Analysis Set)		
14.3.4.6	Summary of Electrocardiogram Results by Visit (Safety Analysis Set)		
14.3.4.7	Shift from Baseline in Electrocardiogram Finding and Overall Impression by Visit (Safety Analysis Set)		
14.3.4.8	Abnormal QTc Interval (ms) by Visit (Safety Analysis Set)		

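### Taking the highest pre-treatment triglyceride as baseline builds an apparent fall of about 4% to 15% into a co-primary endpoint when two draws feed the rule

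*Combined protocol and SAP*

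**What the plan says.** SAP 6.2 and 11.1 define the TG baseline in the same sentence: "Pre-treatment triglyceride level will be defined as the highest value of serum triglyceride at screening visit or baseline visit". The outcome is "Mean change from baseline on serum triglyceride levels at Week 8", expressed as each subject's percent change from that baseline. The rule is absent from protocol section 10.1, where TG is "measured as the difference after 12 weeks of treatment from baseline levels".

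No comparator exists. SAP 7.3 says: "This is an open-label study; therefore, randomization and blinding are not applicable", and the protocol synopsis gives reference therapy as not applicable. Protocol 7.2.1 requires fasting TG above 150 mg/dL at screening.

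The rule covers TG only. For the other lipids and the liver enzymes, SAP 11.3 says "total cholesterol level, liver enzymes (ALT and AST) will be measured by the change from baseline to Week 8 and Week 12", with no highest-value rule and no definition of baseline.

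The documents do not settle which draws count. Table 1 (protocol and SAP) marks the lipid panel at Visit 1 and Visit 2 (one week before Day 1, ± 5 days) but not at Day 1, and the Visit 3 list has none. The synopsis and the opening of protocol 8.8.1.2 describe laboratory tests on Day 1 before dosing.

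**The concern.** A maximum cannot lie below any of the readings it is taken from. Day-to-day and assay variation can therefore only raise the baseline, while the Week 8 value carries ordinary two-sided error. Selecting subjects on TG adds regression to the mean in the same direction, and no control arm is there to subtract either effect.

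The estimate matters because protocol 13.1.3 and SAP 8.1 say the results will feed the design of later studies. In the three placebo-controlled studies summarised in protocol 4.2.1, placebo TG changed by -4.1%, +0.1% and -9.1%. Six of the seven active arms fell by 16.3% to 29.4%, and one rose by 4.5%. An artefact of 4% to 15% is large on that scale.

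**Working it through.** **Plan's own figure.** None exists. The SAP gives no variance, expected change or power for TG, so the check asks what the rule yields when the drug has no effect.

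**Assumed inputs.** Within-subject CV 10% to 30%; correlation ρ between pre-treatment errors 0 or 0.4; on-treatment error independent; log-normal TG with population median 160 to 200 mg/dL and between-subject log-SD 0.4 to 0.5. From the documents: entry above 150 mg/dL, applied here to Visit 1.

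**Step 1: the rule alone, closed form.** For two draws with approximately normal error, E[max] = μ × (1 + CV × √((1 − ρ)/π)). The null fall, as mean endpoint over mean baseline, is 1 − 1/(1 + CV × √((1 − ρ)/π)).

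- CV 10%, ρ = 0.4: 0.10 × √(0.6/π) = 0.0437; fall 4.2%
- CV 20%, ρ = 0: 0.20 × √(1/π) = 0.1128; fall 10.1%
- CV 30%, ρ = 0: 0.30 × √(1/π) = 0.1693; fall 14.5%

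As the mean of per-subject percent changes, which is the SAP's scale, simulation without entry selection gives falls of 3.4% to 8.9%. That is the share due to the rule alone.

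**Step 2: the rule with entry selection, SAP scale.** Simulation with 1,000,000 subjects per scenario and zero drug effect; mean percent change:

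| Baseline | CV 10% | CV 15–30% |
|---|---|---|
| Highest of two, ρ = 0 | -5.5 to -5.1 | -14.6 to -7.3 |
| Highest of two, ρ = 0.4 | -4.5 to -4.0 | -13.2 to -5.8 |
| Highest of three, ρ = 0 | – | -20.0 to -10.9 |
| Highest of three, ρ = 0.4 | – | -17.7 to -8.7 |
| Visit 1 only | about -0.7 to 0 | -4.7 to +0.4 |

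A second simulation with wider populations (median 150 to 250 mg/dL, log-SD 0.4 to 0.6, CV 10% to 30%) gave falls of 3.7% to 15.8% for the highest of two.

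**Step 3: the median.** SAP 8.2 promises it: "Summary statistics for continuous variables will include the number of subjects, the mean, median, standard deviation, and range". For the highest of two at CV 15–30% the median change is -20.1% to -8.9% (ρ = 0) or -19.2% to -7.6% (ρ = 0.4). It shifts further than the mean and so gives no protection.

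**Step 4: alternative baselines.** Geometric mean percent change, CV 15–30%:

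| Baseline | ρ = 0 | ρ = 0.4 |
|---|---|---|
| Highest of two | -20.3 to -9.0 | -19.3 to -7.7 |
| Log-mean of two | -6.1 to -1.0 | -8.3 to -1.5 |
| Visit 2, TG entry on Visit 1 only | about 0 | -4.9 to -0.8 |
| Visit 2, TG entry on Visits 1 and 2 | -8.3 to -1.2 | -10.5 to -1.7 |
| Day 1, TG entry on Visits 1 and 2 | about 0 | -6.2 to -1.0 |

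On the arithmetic scale, a single draw not used for entry gives +2.2% to +9.1% at ρ = 0, because the mean of a ratio is skewed upward. A new baseline therefore needs the log scale as well.

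**The case against.** The strongest reply is that the bias may not arise. Read literally against Table 1, the baseline visit has no lipid panel, so the rule might pick from one value. That is possible, but a highest value then has no meaning, Visit 2 sits under the screening phase with its own lipid panel, and the text describes Day 1 labs. The 4% to 15% remains conditional on two draws.

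The rule is also not responsible for the whole range: alone it gives 3.4% to 8.9% on the SAP's scale, and the rest comes from combining it with selection. CV and correlation are assumed. The higher correlation fits draws taken close together, as Table 1 allows (Visit 1 as late as Day -7). Protocol 7.2.1 instead places the screening liver tests at Day -120 to -30, which is at least 18 days before any Visit 2 (earliest Day -12). The direction does not depend on these inputs.

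On severity, the SAP names no TG test or decision threshold, although SAP 8.3 sets a P-value format ("values will be reported to two digits when"). This is chiefly an estimation problem. By-visit chemistry summaries (Table 14.3.4.3) and subject listings would let a reader compute another baseline. They do not correct the named co-primary result in Table 14.2.1 ("Summary of Serum triglyceride").

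Finally, Day 1 might itself be an entry check, since eligibility is reviewed there. If TG had to exceed 150 mg/dL at all three draws, a Day 1 baseline would keep a geometric bias of -0.9% to -6.5% (ρ = 0) or -1.5% to -10.2% (ρ = 0.4). This is unlikely, because the criterion places confirmation at screening and a central laboratory runs the tests. Even so, the bias would be well below that of the highest-value rule.

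**Conclusion.** The concern holds and must be fixed. Whenever two or more draws feed the rule, the co-primary TG estimate is biased toward benefit. With two draws and entry above 150 mg/dL, the mean fall at zero drug effect is about 4% to 15%, assuming CV 10% to 30% and draw-error correlation 0 to 0.4. With three draws it reaches 20% at the upper end. If only Visit 1 counts, the rule is empty and ordinary regression to the mean remains (mean -4.7% to +0.4% at CV 15–30%). The direction is certain under the two-draw reading; the size rests on assumed variability.

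**What to change.** 1. In SAP 6.2 and 11.1, replace the highest-value rule with one named pre-dose fasting draw, the same for every subject and not used for TG eligibility: Day 1 pre-dose if drawn, otherwise Visit 2. The log-scale mean of all pre-dose draws is an acceptable alternative; it is less noisy but keeps somewhat more residual bias.
2. Analyse log(on-treatment/baseline) and back-transform to percent change with a 95% CI. Adopt this together with step 1, because a single-draw baseline on the arithmetic scale is biased upward.
3. Reconcile three points: whether labs are drawn on Day 1 (synopsis and protocol 8.8.1.2 against Table 1); which draw confirms TG eligibility (protocol 6.1.2 against 7.2.1), since this decides whether Visit 2 is free of selection; and Week 12 in protocol 10.1 against Week 8 in the SAP. The last is a separate discrepancy in the same endpoint.
4. Keep the highest-value result at most as a labelled sensitivity analysis. State that some regression to the mean may remain and that an uncontrolled change cannot be attributed to the drug alone.

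**Cost.** SAP wording and protocol clarifications, with no extra blood draw if Visit 2 is the baseline. The reported fall will look smaller, and one draw is noisier than a mean. The 95% CI factor on the ratio is exp(t × σ × √(f/n)), with σ = √(ln(1 + CV²)), f = 2 for one draw and 1.5 for the mean of two. With independent errors and CV 15–30%, one draw gives ×1.10 to 1.21 at n = 20 and ×1.07 to 1.14 at n = 40; the mean of two gives ×1.09 to 1.18 and ×1.06 to 1.12.

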## 11.2 Cholesterol Efflux Capacity

Cholesterol efflux capacity in the subjects will be quantified at National Institute of Biomedical Innovation, Osaka, Japan using the method previously reported (Ogura et al 2016). Percent efflux will be calculated by the following formula: [( $\mu$ Ci of 3H-cholesterol in mediums containing 2.8% apolipoprotein B–depleted serum – $\mu$ Ci of 3H-cholesterol in serum-free mediums)/ $\mu$ Ci of 3H-cholesterol in cells extracted before the efflux step] × 100. All assays will be performed in duplicate. To correct for inter-assay variation across plates, a pooled serum control from eleven healthy volunteers will be included on each plate, and values for serum samples from patients will be normalized to the value of the pooled sample in subsequent analyses.

### 11.3 Other Secondary Efficacy Analysis

Other secondary measures, lipid profile including serum HDL-C, LDL-C, total cholesterol level, liver enzymes (ALT and AST) will be measured by the change from baseline to Week 8 and Week 12. The percentage (%) of fat in the liver assessed by MRI will be measured by the changes from baseline MRI to post treatment MRI.

# **12 PHARMACOKINETICS ANALYSIS**

Pharmacokinetic parameters of MN-001 and its metabolite, MN-002 will be calculated in a subset of 6 subjects. The following parameters are to be calculated from MN-001/MN-002 plasma concentrations:

Parameter	Description of Parameter
t max	Time from the start of dosing at which the maximum concentration was observed.
C max	Maximum observed concentration.
AUC 0-t	Area under the concentration versus time curve from the start of dose administration to the last quantifiable point within the dosing interval.
$\lambda_z$	Terminal rate constant calculated from the terminal slope of the log-linear regression of concentration with time.
t 1/2	Terminal half-life, calculated as ln (2)/ $\lambda_z$
AUC 0-∞	Area under the concentration versus time curve from time 0 to infinity calculated as $AUC_{0-t} + C_{last}/\lambda_z$ where $C_{last}$ is the last quantifiable concentration.

# **13 SAFETY ANALYSIS**

Safety analyses will be based on the Safety Analysis Set.

## 13.1 Adverse Events

All AEs occurring after the subject signed Informed Consent Form (ICF) will be reported and will be coded using the latest version of MedDRA dictionary.

An overall summary of the number and percentage of subjects with AEs, subjects that lead to discontinuation of study drug, AEs related to study drug (the relationship will be categorized as "related" or "unrelated", where "related" includes investigator terms of "Possibly Related" and "Probably Related"), SAEs, and SAEs related to study drug will be presented by treatment. Also, the AEs will be presented by SOC, PT and treatment. In addition, subjects with AEs in various severity categories (mild, moderate, severe, and life-threatening) will be presented based on the maximum severity of a specific AE for a subject.

Listings of individual by-subject data for any subject experiencing an SAE will be provided separately. All AEs will also be presented in individual by-subject data listings.

#### **13.2** Clinical Laboratory Assessments

For each subject, clinical laboratory parameters including hematology, chemistry will be listed by visit.

